12-lead ECG	X	X	X	X	X	X	X		X	X	X	Triuplicate ECGs will be obtained at screening and predose. Single measurements at 30min, 6hr, 12hr, 24hr, 72hr, 120hr, 168hr post-dose. ECG times may be adjusted once initial PK data is available.

Procedure	Screening (within 28 days of Day 1)	Study Period (Days)									Follow-up (7-14 days following discharge)	Notes
		-1	1	2	3	4	5	6	7	8		
Continuous ECG monitoring			X									Continuous monitoring from -1 hour pre-dose to 24hours post dose. Based on preclinical data levels of parent compound and tryptophan metabolites are expected to reach peak levels within a few hours of the start of dosing. A review of telemetry data will therefore be performed after 24 hours for clinically relevant alerts (see Appendix 9 for guidance). In the absence of such a signal, monitoring will revert to regular ECG assessments. In case clinically relevant changes are observed telemetry will be continued as long as deemed appropriate by the investigator. At the investigator's discretion and in consultation with the medical monitor telemetry could be reinitiated at any time during the study should any potential signals in regular ECG assessments emerge.
Transthoracic Echocardiogram	X											Additional echocardiograms may be performed if increases in cTNI or BNP are observed (see Section 8 for details), or at any time at the discretion of the investigator

Procedure	Screening (within 28 days of Day 1)	Study Period (Days)									Follow-up (7-14 days following discharge)	Notes
		-1	1	2	3	4	5	6	7	8		
Vital Signs	X		X	X	X	X	X				X	VS assessments will be performed in triplicate at screening and at pre-dose. All post dose assessments will be performed as single measurements at 30 min and 1 hr, 6hr, 24hr, 48hr, 72hr, 96hr, 120hr, 144hr, 168hr post-dose as outlined in Section 9.4.2. VS times may be adjusted based on emerging PK data.
Study Treatment			X									
Assessment of infusion site			←-----	-----→								Up to day 8
Blood (PK)			←-----	For sampling time points, see Section 9.5.1-----→						X		Additional blood PK samples may be collected other than those timepoints specified in Section 9.5.1 or on additional days based on emerging data
Urine (metabolism)		X	X									Equivalent to admission on day -1 to pre-dose day 1 and 0-24 hours post-dose as outlined in Section 9.5.2. Part A Cohorts Only.

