
Adverse effects due to reduction of 3 hydroxykynurenone (3HK) levels below the physiological range.
	
KMO deficient mice have undetectable levels of 3HK and elevation of metabolites, such as kynurenone (KYN), kynurenic acid (KYNA) and anthranilic acid (AA), but are viable and healthy. Robust increases in KYN, KYNA, AA and decreases in xanthurenic acid (XA) and quinolinic (QA) were measured in both rats and dogs in the 7-day dose range finding studies. Additionally a robust decrease in 3HK was observed in the dog study. 3HK levels could not be determined in the rat study. However the mid dose used in this rat study had previously been shown to reduce 3HK levels on the first day of dosing in a pharmacology study. Any adverse effects of changes in any of the TRP metabolites, including 3HK, would have been noted in these studies.
 
No information on the dynamics of the pathway after KMO inhibition in man is available and specific data on the rate of recovery of tryptophan metabolites, including 3HK, after
	
General safety monitoring will be conducted throughout the study, dose escalation criteria and stopping criteria (summarized in Appendix 3, Dose Escalation Committee), and a sentinel dosing approach (Section 5.1.1 and Section 5.1.2) have been outlined in the protocol.
 
Based on preliminary PK data from the initial two dose levels in Part A (SAD) a conservative safety observation period of 168 hours after single bolus infusion and after cessation of dosing in the 7-day continuous infusion study in a domiciled setting was chosen; 3HK data from humans is not available yet. The safety observation period will be reassessed based on emerging safety, PK and PD data during the trial.
 
Additional 3HK samples may be collected based on emerging data.

Potential Risk of Clinical Significance	Summary of Data/Rationale for Risk	Mitigation Strategy
	
treatment with GSK3335065 is not available from preclinical studies. Published studies with related KMO inhibitors have shown that recovery of metabolites typically occurs within 24-48hr after a bolus dose in rats (Mole et al 2016; Liddle et al, 2017 although 3HK itself was not measured in these studies.
	

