Treatment Period	For Cohorts 1 and 2, each subject will take part in four dosing session. During each study period subjects will be in-house from the day prior to dosing until Day 4 post dose when they will be discharged after post dose assessments have been completed. Subjects in Cohorts 1 and 2 will return to the unit approximately 3 weeks later to be dosed again on the following day. Following the completion of period 4, subjects will return as out-patients for any post-dose assessments.
Washout Period	Approximately 10 to 21 days between doses ^a .
Follow-up	7-14 days after final study drug administration in the Cohort. If warranted, additional follow-up visits may be scheduled.
Total Duration	Approximately 19 weeks

Table 5 Study Duration of Cohorts 3, 4, 5, 6, 7, 8 (Part A)

Screening	All screening assessments to be completed within 28 days prior to the first dose.
Treatment Period	Each subject will take part in one dosing session. During each study period subjects will be in-house from the day prior to dosing until Day 8 post dose when they will be discharged after post dose assessments have been completed. All subjects may return to the unit approximately 2 weeks after discharge from the unit as out-patients for any post-dose assessments.
Follow-up	Approximately 7-14 days after discharge from the unit. If warranted, additional follow-up visits may be scheduled.
Total Duration	Approximately 7 weeks

5.1.2. Part B: Multiple Ascending Dose (IV Bolus followed by an IV Infusion over 7 days) in Males

Prior to initiation of Part B, a review of all available safety, tolerability, PK and PD data from Part A will be conducted and potential changes to the dosing paradigm, safety observation period and assessments will be communicated in a future amendment to the protocol as appropriate.

Part B is a randomized, placebo-controlled, sequential panel, multiple ascending dose (IV bolus followed by continuous IV infusion over 7 days), double-blind (Sponsor unblinded) trial to evaluate the safety, tolerability, pharmacokinetics and pharmacodynamics of GSK3335065 in healthy male subjects. Subjects will be assigned to one of four Cohorts (9, 10, 11 or 12), and subjects will only participate in one single cohort. In each cohort subjects will be randomized to receive an IV bolus on day 1 subsequently followed by a continuous IV infusion for seven days. of either the active study drug (n=6) or placebo (n=2).

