5.3. Participant and Study Completion

A participant is considered to have completed the study if he/she has completed all phases of the study including last scheduled procedure shown in the Schedule of Activities.

A subject who receives an active dose of study medication and for whom a pharmacokinetic specimens have been collected will be considered an evaluable subject for assessing the pharmacokinetics.

[figure not shown]
The end of the study is defined as the date of the last visit of the last participant in the study.

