The decision to proceed to the next dose level will be based on safety and tolerability data obtained up to 8 days post dose (at discharge from clinical unit) from at least 6 subjects at the prior dose level. The review data set will at a minimum consist of the listings of any adverse events, flagged vital signs, flagged findings during the cardiac monitoring (telemetry) ECG, flagged findings in 12-lead ECGs and laboratory findings (including LFTs, cardiac troponin [cTN], BNP). Available PK data from the prior dose level, together with any available PD data will also be reviewed.

Preliminary PK Data

Estimates of the systemic exposure over 24 hours post-dose, from Part A, Cohorts 1 and 2, were generally consistent with predictions. However, the apparent half-life was significantly longer than the 7.8 hours that had been predicted. Consequently, the PK sampling regimen has been extended to capture the longer terminal phase of elimination.

Preliminary PD Data

Preliminary PD data from Part A to measure the effects of KMO enzyme inhibition showed wide variability in biomarker plasma concentrations both at baseline and during treatment, and included the following biomarkers of the tryptophan pathway: Kynurenine (Kyn), 3-hydroxykynurene (3-HK), tryptophan, kynurenic acid, anthranilic acid, 3-hydroxyanthranilic acid, quinolic acid and xanthurenic acid. To enable a reliable assessment of baseline levels and their underlying variability, as well as to ensure all

subjects are in a similar physiological state upon receiving the dose allowing time for any uncontrolled external influences on biomarker levels (food intake, meal time, sleep cycle) to dissipate, subjects will be enrolled at least 12 hours prior to dosing, eg. the afternoon of the day prior to the dose. Blood samples for the measurement of tryptophan pathway biomarkers will be taken regularly. Sleep disruption will be avoided, as it may perturb biomarker levels from their natural levels. On the day prior to dosing (day -1), the proposed sample times are as follows: -16hrs, -14hrs, -12hrs and 10hrs followed by -2hrs and approximately 0.5hrs predose on the day of dosing. (day 1). Flexibility around these nominal times will be permitted.

Highest Dose in Part A

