6.1. Inclusion Criteria

Participants are eligible to be included in the study only if all of the following criteria apply:

Age

1. Participant must be 18 to 50 years of age inclusive, at the time of signing the informed consent. In Part C (WONCBP) participants must be between 18 and 60 years of age.

Type of Participant and Disease Characteristics

2. Participants who are overtly healthy as determined by medical evaluation including medical history, physical examination, laboratory tests, and cardiac monitoring.
3. A subject with a clinical abnormality or laboratory parameter(s) which is/are not specifically listed in the inclusion or exclusion criteria, outside the reference range for the population being studied may be included only if the investigator in consultation with the Medical Monitor if required agree and document that the finding is unlikely to introduce additional risk factors and will not interfere with the study procedures.

Weight

4. Body weight >50kg and body mass index (BMI) within the range 18.5 – 32 kg/m² (inclusive).

Sex

5. Abstinence/contraceptives: Length of time required for abstinence or use of contraceptives should take into account the reproductive toxicity profile including genotoxicity and teratogenicity, the size of the molecule, and the number of doses.

a. Male participants:

A male participant must agree to use contraception as detailed in [Appendix 5](#) of this protocol during the treatment period and for at least 2 days after the last dose of study treatment and refrain from donating sperm during this period.

b. Female participants:

Only female participants of non childbearing potential (WONCBP) as defined in [Appendix 5](#): Contraceptive Guidance and Collection of Pregnancy Information are eligible to participate.

Informed Consent

6. Capable of giving signed informed consent as described in [Appendix 3](#) which includes compliance with the requirements and restrictions listed in the informed consent form (ICF) and in this protocol.

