9.3. Treatment of Overdose

For this study, any dose of GSK3335065 greater than the agreed dose for a particular cohort, dosing session or study part will be considered as an overdose.

GSK does not recommend specific treatment for an overdose

In the event of an overdose the investigator or treating physician should:

1. Contact the Medical Monitor immediately
2. Closely monitor the subject for adverse events (AEs)/serious adverse events (SAEs) and laboratory abnormalities until GSK3335065 can no longer be detected systemically (at least 8 days which is equivalent to 5 times the observed preliminary half life of ~35 hours for GSK3335065).
3. Obtain a plasma sample for pharmacokinetic (PK) analysis within 1 days from the date of the last dose of study treatment if requested by the Medical Monitor (determined on a case-by-case basis)

4. Document the quantity of the excess dose as well as the duration of the overdosing in the CRF.

Decisions regarding dose interruptions or modifications will be made by the investigator in consultation with the Medical Monitor based on the clinical evaluation of the subject.

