12.5. Appendix 5: Contraceptive Guidance and Collection of Pregnancy Information

Definitions

Woman of Childbearing Potential (WOCBP)

A woman is considered fertile following menarche and until becoming post-menopausal unless permanently sterile (see below)

Women in the following categories are not considered WOCBP

1. Premenopausal female with ONE of the following:

- Documented hysterectomy
- Documented bilateral salpingectomy
- Documented bilateral oophorectomy
- Documented tubal ligation

Note: Documentation can come from the site personnel's: review of participant's medical records, medical examination, or medical history interview.

2. Postmenopausal female

- A postmenopausal state is defined as no menses for 12 months without an alternative medical cause. A high follicle stimulating hormone (FSH) level in the postmenopausal range may be used to confirm a postmenopausal state in women not using hormonal contraception or hormonal replacement therapy (HRT). However, in the absence of 12 months of amenorrhea, a single FSH measurement is insufficient.
- Females on HRT and whose menopausal status is in doubt will not be allowed in the study.

Contraception Guidance

Male participants

- Male participants with female partners of child-bearing potential are eligible to participate if they agree to ONE of the following during the duration of the study and for at least 2 days from last dose:
 - Are abstinent from penile-vaginal intercourse as their usual and preferred lifestyle (abstinent on a long term and persistent basis) and agree to remain abstinent
 - Agree to use a male condom plus an additional method of contraception with a failure rate of <1% per year when having penile-vaginal intercourse with a woman of childbearing potential
- Men with a pregnant or breastfeeding partner must agree to remain abstinent from penile-vaginal intercourse or use a male condom during each episode of

penile penetration during the duration of the study and for at least 2 days from last dose.

- Refrain from donating sperm for duration of study and for at least 2 days from last dose

Collection of Pregnancy Information

Male participants with partners who become pregnant

- Investigator will attempt to collect pregnancy information on any male participant's female partner of a male study participant who becomes pregnant while participating in this study. This applies only to participants who receive study treatment.

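### The 2-day minimum for male contraception is only about 1.4 half-lives at the observed ~35 h, and no section says when the duty ends for a man who leaves early

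*Protocol*

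**What the plan says.** Protocol 6.1, criterion 5a, requires male contraception and no sperm donation "during the treatment period and for at least 2 days after the last dose of study treatment". It refers to Appendix 5 (Section 12.5) for the detail, where the period is worded differently: "during the duration of the study and for at least 2 days from last dose". Appendix 5 applies the same two-part period to sperm donation.

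On pharmacokinetics, Section 5.4.1 reports from Cohorts 1 and 2 that "the apparent half-life was significantly longer than the 7.8 hours that had been predicted". Section 9.3 gives a value, asking for monitoring after an overdose for "at least 8 days which is equivalent to 5 times the observed preliminary half life of ~35 hours". Other parts of the protocol follow the new information:

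- Section 3.3.1 uses the preliminary PK data to set "a conservative safety observation period of 168 hours after single bolus infusion and after cessation of dosing".
- Table 5 in Section 5.1.1 keeps men in Cohorts 3 to 8 "in-house from the day prior to dosing until Day 8 post dose when they will be discharged". Table 4 had Cohorts 1 and 2 leaving at Day 4.
- Section 9.5.1 extends PK sampling from 72 h (Cohorts 1 and 2) to 168 h (Cohorts 3 to 8).

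The amendment history (Section 12.10), used here only for dating, places the 2-day figure in the protocol body by July 2017, before these data existed.

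**The concern.** The minimum is the same number of days as before, but it now covers a much smaller part of the drug's elimination. Neither 6.1 nor Appendix 5 explains why 2 days remains enough.

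The number matters only for men who leave early. Early exit is provided for: Section 8.2 lets a man leave at any time, and Sections 8.1.2 and 8.1.4 require withdrawal or discontinuation on QTc and cardiac-marker criteria. For such a man the 2 days is the only explicit figure. Sections 8.1.2 and 8.2 send leavers to the Schedule of Activities, which has no early-withdrawal column. The two wordings also disagree, since a treatment period is shorter than the duration of a study.

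What is at stake is a precaution for partners, not any endpoint. Section 3.1 excludes women of childbearing potential because reproductive assessment is limited, and Section 3.3.1 lists inflammatory foci in rat testis and prostate.

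**Working it through.** **Inputs.** Minimum 2 days = 48 h (6.1, Appendix 5). Predicted half-life 7.8 h, volume 27 L and clearance 2.4 L/h (5.4.1). Observed half-life ~35 h and 8 days (9.3).

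**The plan's own figures.** Predicted half-life = ln 2 × 27 / 2.4 = 7.8 h, as stated. Five observed half-lives = 5 × 35 = 175 h = 7.3 days, which rounds up to the stated 8 days.

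**What 2 days covers.** The fraction remaining is 0.5^(48/half-life), assuming mono-exponential decline.

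- At 7.8 h: 48/7.8 = 6.2 half-lives, about 1.4% remaining.
- At 35 h: 48/35 = 1.4 half-lives, about 39% remaining.

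**Men who complete follow-up.** In Part A, discharge is at 168 h and follow-up is 7 to 14 days later, so cover runs to (168 + 168)/35 = 9.6 up to (168 + 336)/35 = 14.4 half-lives. In Part B, the infusion ends on Day 8 and follow-up is on Day 32 ± 2, which is 22 to 26 days later: 528/35 = 15.1 to 624/35 = 17.8 half-lives. Neither group has a shortfall.

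**Men who leave early.** Assume the duty ends at exit or at 2 days, whichever is later. For exit x days after the last dose, explicit cover is max(2, x) days. The gap is 8 − max(2, x) days against Section 9.3, and 175 − 24 × max(2, x) hours against exactly 5 half-lives.

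| Exit, days after last dose | Gap to 8 days | Gap to 175 h |
|---|---|---|
| up to 2 | 6 days | 127 h (5.3 days) |
| 3 | 5 days | 103 h (4.3 days) |
| 4 | 4 days | 79 h (3.3 days) |
| 5 | 3 days | 55 h (2.3 days) |
| 6 | 2 days | 31 h (1.3 days) |
| 7 (Day 8 discharge, Part A) | 1 day | 7 h (0.3 days) |
| 8 or more | 0 | 0 |

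**Sensitivity.** The half-life is given only approximately. Over an assumed range of 30 to 40 h, five half-lives is 6.25 to 8.33 days, and the largest gap is 4.25 to 6.33 days.

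**Timing of checks.** The Part A ECG schedule reads "Single measurements at 30min, 6hr, 12hr, 24hr, 72hr, 120hr, 168hr post-dose". Five of the seven fall within 72 h, where the gap to 8 days would be 5 or 6 days. This shows when a QTc withdrawal could first be triggered. It does not show how many men would leave, which is not known.

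**The case against.** The strongest reply is that the text already covers everyone. Criterion 5a defers to Appendix 5, whose two conditions both apply, and Section 5.3 says "The end of the study is defined as the date of the last visit of the last participant in the study". Read literally, that binds an early leaver well past 8 days. This stands as a possible reading. But Section 5.3 defines the end of the trial, and nothing says it is meant to set an individual's contraception duty after he has left. Criterion 5a also states its own, shorter period.

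Second, the 8 days belongs to overdose monitoring. That is correct, so it serves only by analogy. Five half-lives does appear elsewhere as an element of washout rules: exclusion 8, Section 7.8, and the treatment-emergent window in SAP 11.4.2.

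Third, a reader might infer that 2 days was calculated from 7.8 h and then overlooked. The documents do not support this. Criterion 5 names reproductive toxicity, molecule size and number of doses as the determinants, not half-life. The amendment history records only that the appendix was aligned to the body at the regulator's request. All that can be said is that the number is unchanged and not re-justified.

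Fourth, the supporting toxicology is in the Investigator's Brochure, which is not among the documents, and the consent pages were removed from the copy reviewed. Either may settle the matter. Section 3.3.1 also states a 75-fold NOAEL margin for the rat foci.

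Fifth, few men may be affected. Meeting a cardiac criterion brings repeat testing or consultation, not necessarily departure from the unit.

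**Conclusion.** The point holds as a minor, precautionary one. The explicit minimum has fallen from 6.2 to about 1.4 half-lives, and the text does not say when the duty ends for a man who leaves early. The maximum shortfall is 5.3 days against 5 half-lives, or 6 days against Section 9.3. It applies only to exit within 2 days of the last dose, and only if the duty lapses at exit or at 2 days.

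Two stronger conclusions are tempting and should not be drawn. Criterion 5a alone might suggest that every man is released after 2 days, but Appendix 5 extends the duty for men who complete the study. Nor do the documents show that 2 days is harmful.

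The SAP introduction records termination after sentinel dosing in Cohort 3, so the change bears on the protocol as planned or on any resumption, not on data already collected.

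**What to change.** In protocol 6.1 criterion 5a and in Appendix 5, use one sentence for both contraception and sperm donation: *for the duration of the study and in any case for at least 8 days after the last dose, including after early withdrawal or discontinuation*. Carry it into the consent form if that repeats the 2 days. If the sponsor prefers to keep 2 days, cite the Investigator's Brochure data that support it at a half-life of ~35 h. SAP Appendix 1 should stay as it is, since it reproduces the enrolment criteria.

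The cost is wording in two protocol sections, and possibly the consent form, for the 6 × 8 + 4 × 8 = 80 men planned in Cohorts 3 to 12. Early leavers would carry the restriction for up to about 6 more days. Men who complete follow-up would carry nothing beyond what Appendix 5 already asks.

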6.2. Exclusion Criteria

Participants are excluded from the study if any of the following criteria apply:

Medical Conditions

1. Alanine transaminase (ALT) and bilirubin >1.5xULN (isolated bilirubin >1.5xULN is acceptable if bilirubin is fractionated and direct bilirubin <35%).
2. Current or chronic history of liver disease, or known hepatic or biliary abnormalities (with the exception of Gilbert's syndrome or asymptomatic gallstones)

3. QTcF >450 msec from a mean of triplicate readings taken no more than 2 minutes apart
4. Clinically significant abnormal echocardiogram
5. The participant has a history or current evidence of depression, bipolar disorder, suicidal ideation and behaviour, or a lifetime history of suicide attempt.
6. cTn or BNP >ULN

Prior/Concomitant Therapy

7. Use of prohibited medication (Section 7.7 & Section 7.8)

Prior/Concurrent Clinical Study Experience

8. The subject has participated in a clinical trial and has received an investigational product within the following time period prior to the first dosing day in the current study: 30 days, 5 half-lives or twice the duration of the biological effect of the investigational product (whichever is longer).
9. Exposure to more than four new chemical entities within 12 months prior to the first dosing day

Diagnostic assessments

10. Presence of hepatitis B surface antigen (HBsAg), positive hepatitis C antibody test result at screening or within 3 months prior to first dose of study treatment. For potent immunosuppressive agents, subjects with presence of hepatitis B core antibody (HBcAb) should also be excluded.
11. A positive pre-study drug/alcohol screen.
12. A positive test for human immunodeficiency virus (HIV) antibody.
13. Where participation in the study would result in donation of blood or blood products in excess of 500 mL within 84 days.

Other Exclusions

14. Poor or unsuitable venous access
15. History of regular alcohol consumption within 6 months of the study defined as:
An average weekly intake of >14 units. One unit is equivalent to 8 g of alcohol: a half-pint (~240 mL) of beer, 1 glass (125 mL) of wine or 1 (25 mL) measure of spirits.
16. History of sensitivity to any of the study medications, or components thereof or a history of drug or other allergy that, in the opinion of the investigator or Medical Monitor, contraindicates their participation.
17. History of smoking within 6 months of the study.

